8. OVERVIEW OF MOLECULAR INVESTIGATIONS

- mRNA signature in tumor tissue pre- and post-therapy by whole transcriptome sequencing using RNAseq (by a lab such as Rutgers CINJ)
- Genomic profiling of metastatic and primary tumor DNA (by a lab such as FoundationOne®)
- CEA and MUC-1 antigen-specific immune response in pre- and post-therapy in peripheral blood by intracellular cytokine staining and/or ELISPOT or other validated assays.
- Other tumor-associated antigen-specific immune response measures may be assessed if adequate samples are available (by a lab such as [name] lab, NIH)
- TCR clonality assays (by a lab such as Adaptive Biotechnologies®)
- Serum cytokine, and serum soluble factors (by a lab such as [name] lab, NIH)
- PD-1/PD-L1 staining in pre- and post-therapy tumor tissue (by a lab such as Rutgers CINJ or Neogenomics)
- Immunoscore by IHC to be performed at a lab such as Rutgers CINJ

8.1 Tissue

8.1.1 Tissue prior to Treatment

A pre treatment tumor biopsy is required. The goal of collection is 50 mg of tumor tissue to be used for correlative testing. The site investigator and interventional radiologist should discuss the amount of cores that may be necessary to meet the goal of tissue collection. The pre-treatment biopsy is required regardless of prior biopsy confirmation of metastatic CRC.

Genomic testing results are required. FoundationOne platform is preferred, however results from an equivalent genomic platform may be used after discussion with the sponsor investigator. If genomic testing has not been performed, tissue should be submitted for testing per standard of care.

8.1.2 Surgical Tissue or Tissue from Biopsy

After neoadjuvant therapy, additional tissue will be obtained either at the time of surgery, or with a repeat biopsy if the patient is not a candidate for surgery, prior to further systemic or radiation treatment for the above mentioned correlates. There will be a cap of 10 fresh biopsies for unresectable subjects. The ideal amount of tumor tissue is 50 mg to be utilized for correlative analysis. The amount of cores to obtain this tissue is dependent on the type of core biopsy needle used. The site investigator should discuss this requirement with the appropriate physician performing the procedure.

Collection procedures will take place at individual participating institutions. Handling procedures will be performed according to participating site standard operating procedures (SOPs). Detailed shipping information regarding which specimens and the location for shipping are provided in the correlative laboratory manual (CLM). Shipping will be done in batches at intervals to be determined.

8.2 Peripheral Blood

Patients will have peripheral blood draws for isolation of peripheral blood mononuclear cells (PBMCs). Peripheral blood will be drawn (1) before vaccination on Day -28 (Arm B) or before Cycle 1 Day 1 (Arm A), (2) before surgery (both Arms), (3) one month after surgery for the above-mentioned correlates (both Arms) and (4) six months after surgery (both Arms).

Peripheral blood for PBMCs will be collected and then shipped unprocessed overnight by all participating sites. PBMCs will be isolated. Serum will be collected and shipped for cytokine analysis.

Whole blood will be sent for isolation of genomic DNA for TCR clonality assays before vaccination (ARM B)/Treatment (ARM A), and 1 month post-surgery.

Whole blood will be collected for genomic DNA prior to treatment for both Arms (Day -28 Arm B and Cycle 1 Day 1 Arm A).

8.3 Storage of Biospecimens

Any remaining samples after initial testing is done will be stored for future unspecified cancer related research. Permission to use these samples will be obtained from subjects during consent.

8.4 Confidentiality of Biospecimens

Samples that are collected will be identified by a subject's sequence ID assigned at the time of registration to the trial. Any material issued to collaborating researchers will be anonymized and only identified by the subject's study number.

9. CRITERIA FOR DISEASE EVALUATION

9.1 Measurable Disease

Measurable disease is defined as the presence of at least one measurable lesion. Measurable lesions are defined as those that can be accurately measured in at least one dimension (longest diameter to be recorded) as ≥ 20 mm by chest x-ray, as ≥ 10 mm with CT scan, or ≥ 10 mm with calipers by clinical exam. All tumor measurements must be recorded in millimeters (or decimal fractions of centimeters).

9.1.1 Malignant Lymph Nodes

To be considered pathologically enlarged and measurable, a lymph node must be ≥ 15 mm in short axis when assessed by CT scan (CT scan slice thickness recommended to be no greater than 5 mm). At baseline and in follow-up, only the short axis will be measured and followed.

9.2 Non-measurable Lesions

All other lesions (or sites of disease), including small lesions (longest diameter < 10 mm or pathological lymph nodes with ≥ 10 to < 15 mm short axis), are considered non-measurable disease. Bone lesions, leptomeningeal disease, ascites, pleural/pericardial effusions, lymphangitis cutis/pulmonitis, inflammatory breast disease, and abdominal masses (not followed by CT or MRI), are considered as non-measurable.

NOTE: Cystic lesions that meet the criteria for radiographically defined simple cysts should not be considered as malignant lesions (neither measurable nor non-measurable) since they are, by definition, simple cysts. ‘Cystic lesions’ thought to represent cystic metastases can be considered as measurable lesions, if they meet the definition of measurability described above. However, if non-cystic lesions are present in the same subject, these are preferred for selection as target lesions.

9.3 Target Lesions

All measurable lesions up to a maximum of 2 lesions per organ and 5 lesions in total, representative of all involved organs, should be identified as target lesions and recorded and measured at baseline. Target lesions should be selected on the basis of their size (lesions with the longest diameter), be representative of all involved organs, but in addition should be those that lend themselves to reproducible repeated measurements. It may be the case that, on occasion, the largest lesion does not lend itself to reproducible measurement in which circumstance the next largest lesion which can be measured reproducibly should be selected. A sum of the diameters (longest for non-nodal lesions, short axis for nodal lesions) for all target lesions will be calculated and reported as the baseline sum diameters. If lymph nodes are to be included in the sum, then only the short axis is added into the sum. The baseline sum diameters will be used as reference to further characterize any objective tumor regression in the measurable dimension of the disease.

9.4 Non-target Lesions

All other lesions (or sites of disease) including any measurable lesions over and above the 5 target lesions should be identified as non-target lesions and should also be recorded at baseline. Measurements of these lesions are not required, but the presence, absence, or in rare cases unequivocal progression of each should be noted throughout follow-up.

9.5 Evaluation of Target Lesions

NOTE: See the international criteria proposed by the Response Evaluation Criteria in Solid Tumors (RECIST) Committee, version 1.1 for special notes on the assessment of target lesions²¹.

Complete Response (CR)	Disappearance of all target lesions. Any pathological lymph nodes (whether target or non-target) must have reduction in short axis to <10 mm.
Partial Response (PR)	At least a 30% decrease in the sum of the diameters of target lesions, taking as reference the baseline sum diameters
Stable Disease (SD)	Neither sufficient shrinkage to qualify for PR nor sufficient increase to qualify for PD, taking as reference the smallest sum diameters while on study
Progressive Disease (PD)	At least a 20% increase in the sum of the diameters of target lesions, taking as reference the smallest sum on study (this includes the baseline sum if that is the smallest on study). In addition to the relative increase of 20%, the sum must also demonstrate an absolute increase of at least 5 mm. (Note: the appearance of one or more new lesions is also considered progressions).

9.6 Evaluation of Non-Target Lesions

Complete Response (CR)	Disappearance of all non-target lesions and normalization of tumor marker level. All lymph nodes must be non-pathological in size (<10 mm short axis) NOTE: If tumor markers are initially above the upper normal limit, they must normalize for a subject to be considered in complete clinical response.
Non-CR/ Non-PD	Persistence of one or more non-target lesion(s) and/or maintenance of tumor marker level above the normal limits
Progressive Disease (PD)	Appearance of one or more new lesions and/or unequivocal progression of existing non-target lesions. Unequivocal progression should not normally trump target lesion status. It must be representative of overall disease status change, not a single lesion increase.

Although a clear progression of “non-target” lesions only is exceptional, the opinion of the site investigator should prevail in such circumstances, and the progression status should be confirmed at a later time by the sponsor-investigator.

Subjects with a global deterioration of health status requiring discontinuation of treatment without objective evidence of disease progression at that time should be classified as having “symptomatic deterioration.” Every effort should be made to document the objective progression even after discontinuation of treatment.

In some circumstances, it may be difficult to distinguish residual disease from normal tissue. When the evaluation of complete response depends on this determination, it is recommended that the residual lesion be investigated (fine needle aspirate/biopsy) to confirm the complete response status.

9.7 Definitions for Response Evaluation

9.7.1 Overall Survival

For the primary objective OS is defined as the date of metastasectomy to date of death from any cause.

9.7.2 Objective Response Rate

The objective response rate is the proportion of all subjects with confirmed PR or CR according to RECIST 1.1 and surgical pathology defined as the percent tumor viability (see 9.7.3 for definition), from the start of treatment until disease recurrence.

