2.2 Secondary Objectives

- Compare 3- year recurrence-free survival (RFS) between the experimental and control treatment groups.
- Compare 3-year OS between the experimental and control groups
- Compare OS (in both the experimental and control groups) to historical controls
- Evaluate the best overall response rates (both by RECIST 1.1 and surgical pathology) between the experimental and control groups.

- Compare the pathologic complete response rate to neoadjuvant therapy in resected tumor tissue between the experimental and control groups.
- In patients who experience a recurrence after surgery, evaluate the proportion of patients amenable to complete re-resection/ablation between the experimental and control treatment groups.
- In patients who experience a recurrence after protocol therapy, compare the progression free survival post-recurrence between the experimental and control groups.
- Evaluate the perioperative surgical outcomes (complications and severity scores) between the experimental and control groups.
- Compare 3-year OS from the date of registration between experimental and control groups

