5.1.3 Surgical Resection

About 2 weeks after neoadjuvant therapy, patients will be re-evaluated for surgical resection with re-staging imaging of the C/A/P. Patients still considered resectable will undergo surgical resection about 4 weeks after completion of neoadjuvant therapy. The goal of surgical resection is completely treating all of their disease by either resection and/or ablation. Patients with bilobar disease must have all of their disease treated in a single operation. Synchronous primary

colorectal and metastatic hepatic tumors are eligible, provided all disease can be resected in a single operation. We will collect peripheral blood and tumor tissue at the time of surgical resection, if applicable, or by re-biopsy if resection is not possible.

Patients deemed unresectable will be managed according to their individual cancer center's disease group management team and will continue to receive Nivolumab (Arm A and Arm B) +/- vaccine (Arm B) as described below. There is no delay required to proceed with study treatment.

In the event that administration of nivolumab +/- the vaccine is impacting the delivery or tolerability of standard of care therapy, patients will be removed from protocol therapy but will continue to be followed on study.

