5.1.4 Adjuvant Therapy

Once patients in the post-operative period are deemed ready to begin therapy (about 6-8 weeks after surgery) or for those subjects that are deemed unresectable and continue with treatment:

- Patients in the control arm (Arm A) will receive 8 cycles of mFOLFOX6 in addition to nivolumab given every 2 weeks through completion of chemotherapy: Cycle 5 – Cycle 12. The treatment order for Arm A is Nivolumab followed by mFOLFOX6.
- Patients in the experimental arm (Arm B) will receive 8 cycles of mFOLFOX6 in addition to nivolumab and FPV-CV301 boosters given every 2 weeks through completion of chemotherapy: Cycle 5 - Cycle 12. For Arm B the order of administration is Nivolumab followed by the vaccination at least one hour prior to mFOLFOX6.

If possible, nivolumab (Arm A and Arm B) +/- the CV301 (Arm B) will be administered on the day (+2 days) that systemic chemotherapy resumes. We will re-collect peripheral blood for evaluation of correlates per the study calendar. For Arm B the order of administration is Nivolumab followed by the vaccination at least one hour prior to mFOLFOX6. A window of +2 days between administration of Nivolumab +/- vaccination and mFOLFOX6 will be allowed. This window will accommodate subjects that receive their chemotherapy locally. If there is more than a 2-day delay for any reason, administration of study drugs should be re-aligned so that the chemotherapy falls within +2 days with the next cycle.

In the event that patients in the experimental arm suffer complications that render them unfit for adjuvant systemic chemotherapy or that they cannot complete their adjuvant systemic chemotherapy due to toxicity, patients will still be eligible to receive their scheduled nivolumab and/or CV301 provided the investigators deem them fit enough to do so.

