6: Patients that are registered must have confirmed isolated liver metastases by radiographic imaging. Baseline imaging must include the chest, abdomen, and pelvis by CT, PET/CT or triphasic CT. Re-staging imaging after neoadjuvant therapy to include CT, PET/CT or triphasic CT of the chest, abdomen/pelvis. Additional imaging required for surgical evaluation is at the surgical oncologist's discretion and can include an MRI in addition to restaging scans. Response will be assessed (1) prior to surgery/after 4 cycles of neoadjuvant therapy and (2) at completion of adjuvant therapy. Upon completion of adjuvant therapy, repeat imaging should occur every 3 months during maintenance. After completion of maintenance, imaging should occur every 3 months for 2 years followed by every 6 months for up to an additional year (total 3 years). The modality used for disease evaluation should be consistent throughout the study period.

7: Detailed description of study treatment can be found in Section 5. Arm A is the control arm and Arm B is the experimental arm. Post-surgery therapy will begin when the surgical oncologist deems the patient is ready and is clear of all infectious issues. For those subjects that do not undergo resection, post-surgery therapy may begin at treating physician discretion. The treatment order for Arm A is Nivolumab followed by mFOLFOX6. For Arm B the order of administration is vaccination prior to the start of nivolumab at least one hour prior to mFOLFOX6. A window of +2 days between administration of Nivolumab ± vaccination and mFOLFOX6 will be allowed. This window will accommodate subjects that receive their chemotherapy locally. If there is more than a 2-day delay for any reason, administration of study drugs should be re-aligned so that the chemotherapy falls within +2 days with the next cycle.

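### Objective response covers all subjects in 9.7.2 but falls under the resected-only efficacy rule in 12.6, and its window does not close at surgery

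*Combined protocol and SAP*

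**What the plan says.** **Definition.** Section 9.7.2: "The objective response rate is the proportion of all subjects with confirmed PR or CR according to RECIST 1.1 and surgical pathology". The period is "from the start of treatment until disease recurrence". The matching objective in 2.2, repeated in the Synopsis, is: "Evaluate the best overall response rates (both by RECIST 1.1 and surgical pathology) between the experimental and control groups". Section 12.2.2 lists best overall response among the secondary endpoints.

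**Assessments.** Study Calendar footnote 6: "Response will be assessed (1) prior to surgery/after 4 cycles of neoadjuvant therapy and (2) at completion of adjuvant therapy". Between those two points comes an operation aimed at "completely treating all of their disease by either resection and/or ablation" (5.1.3). The adjuvant phase is also open "for those subjects that are deemed unresectable and continue with treatment" (5.1.4).

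**Scoring.** For target lesions, complete response (CR) is "Disappearance of all target lesions" (9.5). Section 9.6 adds conditions on non-target lesions and markers, including: "If tumor markers are initially above the upper normal limit, they must normalize for a subject to be considered in complete clinical response".

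**Analysis sets.** Section 12.6 restricts efficacy evaluation to patients with at least one dose who were completely resected. Section 12.4 defines Enrolled, Per Protocol and Treated sets but assigns none to response. Section 12.7 names the resected set only for Kaplan-Meier estimation of RFS and OS. Section 12.3 plans 70 resected patients from 74 enrolled, rising to 78 if needed, and attributes non-resection to progression or complications of neoadjuvant therapy. The Synopsis (Study Design) replaces each patient who cannot be completely resected with another in the same arm.

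**The concern.** Two analysts could each follow the document and report different response rates. One would divide by everyone enrolled, the other by the completely resected.

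The second choice is more than a smaller denominator. Whether a patient reaches resection is decided after randomization and partly by the neoadjuvant treatment under comparison. Removing those who fail, and refilling each arm to about 35 resected patients, can hide an arm difference in that failure.

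The window raises a separate problem. The second scheduled response assessment comes after the lesions have been removed or ablated. If such a scan can supply a best response of CR, the endpoint mixes what the surgeon achieved with what the drugs achieved.

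**Working it through.** **1. The plan's own figure.** Inputs from 12.3: 70 resected, about 5% not resected. 70 / 0.95 = 73.7, rounded up to 74, which agrees with the plan. The competing denominators are therefore 74 to 78 and about 70. The gap is 4 to 8 patients (4/74 = 5.4%; 8/78 = 10.3%).

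**2. Effect on the overall rate.** The documents give no response rate, so 30% to 60% among resected patients is assumed, with unresected patients as non-responders. Drop = r × (1 − 70/N).

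| Assumed r (of 70) | N = 74 | Drop (points) | N = 78 | Drop (points) |
|---|---|---|---|---|
| 30% (21) | 28.4% | 1.6 | 26.9% | 3.1 |
| 40% (28) | 37.8% | 2.2 | 35.9% | 4.1 |
| 60% (42) | 56.8% | 3.2 | 53.8% | 6.2 |

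The drop is smaller if some patients kept from surgery by complications had responded.

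**3. Effect on the arm comparison.** Assume 14/35 = 40% response among resected patients in each arm. The resected set then shows no difference, by construction. Over all enrolled patients:

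| Unresected, split by arm | Rates | Difference (points) |
|---|---|---|
| 4, as 3:1 | 14/38 = 36.8% vs 14/36 = 38.9% | 2.0 |
| 8, as 6:2 | 14/41 = 34.1% vs 14/37 = 37.8% | 3.7 |
| 8, as 8:0 | 14/43 = 32.6% vs 14/35 = 40.0% | 7.4 |

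For scale, the standard error of a difference at 40% with 35 per arm is √(2 × 0.4 × 0.6 / 35) = 11.7 points.

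**4. When the second assessment falls.** Section 5.1.4 restarts treatment about 6 to 8 weeks after surgery and gives 8 two-week cycles: 6 to 8 + 16 = 22 to 24 weeks after the operation.

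**5. What the window depends on.** Section 9.7.2 joins RECIST and surgical pathology with a bare conjunction.
- If both must be met, clearance on a scan cannot turn a patient with fully viable tumor into a responder.
- If they are two rates, as the objective in 2.2 suggests, the RECIST rate has no such protection.

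The joint reading is hard to apply to all subjects. Section 9.7.3 sets no viability cut-off for partial response (PR), and unresected patients have no resection specimen, only a research biopsy subject to a cap of 10 (8.1.2).

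**6. Direction of the window effect (illustration).** Let pA and pB be the true response in the control and experimental arms among resected patients, and fA and fB the share of resected non-responders credited with a post-operative CR. The observed rate is p + f(1 − p), so

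observed difference = (pB − pA) + fB(1 − pB) − fA(1 − pA).

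For assumed true rates of 40% vs 60% (20 points):

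| fA | fB | Observed rates | Difference (points) |
|---|---|---|---|
| 0.10 | 0.10 | 46% vs 64% | 18 |
| 0.25 | 0.25 | 55% vs 70% | 15 |
| 0.10 | 0.25 | 46% vs 70% | 24 |
| 0.25 | 0.10 | 55% vs 64% | 9 |

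Equal shares always shrink the difference, by the factor 1 − f. With unequal shares it can grow: here, whenever 0.4 × fB exceeds 0.6 × fA, that is, fB > 1.5 × fA. Credit requires being free of recurrence at that scan, which the vaccine could affect, so equal shares cannot be presumed.

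**The case against.** **The denominator may already be settled.** Section 9.7.2 is the specific definition, 12.6 is a general statement, and 12.7 applies the resected set by name only to RFS and OS. An analyst could reasonably let 9.7.2 govern. That reading is available, but 12.6 contains no exception and 12.4 assigns no set to response, so it needs to be written down. For pathology the objection stands: resected patients are the natural descriptive denominator.

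**The numbers are small.** This is correct. Every shift in the tables lies below the 11.7-point standard error. The 7.4-point case needs all 8 unresected patients in one arm, which under equal failure risk has probability 2/256 = 0.8%. The endpoint carries no power or alpha.

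**Stronger readings of the window.** A reader might infer that the protocol counts surgical removal as CR, which at the extreme would give 70/78 = 89.7% to 70/70 = 100% whatever the true response. The documents do not support this. No section says removal counts, the conditions in 9.6 must also be met, and 9.5 refers to RECIST 1.1 for special notes that are not reproduced. What can be said is that the protocol's own text does not exclude it. Nor may a reader infer that the effect always dilutes an arm difference; step 6 shows otherwise. The later scan also has proper uses: recurrence in resected patients and response in unresected patients still on treatment.

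**Confirmation.** A reader might infer that the plan has no confirmation text at all. Section 9.6 does recommend aspirate or biopsy of a doubtful residual lesion to establish CR. That does not cover PR, and resected patients have only one scheduled post-baseline response assessment with lesions in place.

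**Conclusion.** The denominator conflict holds with high confidence. Sections 9.7.2 and 12.6 give sets that differ by 4 to 8 patients, and the 12.6 set selects on a post-randomization outcome of the therapy being compared. The overall rate moves by 1.6 to 6.2 points, assuming 30% to 60% response and no responders among unresected patients. This is a systematic effect, but small against sampling error.

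The window problem holds with medium confidence. It depends on the RECIST rate standing alone, its size cannot be derived from the documents, and its direction is not fixed.

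Overall the point is minor to moderate. It concerns one unpowered secondary endpoint. Pathologic complete response remains a separate objective, and neither the primary OS test nor the sample size is affected.

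**What to change.** For the between-arm comparison:
- Define RECIST response as PR or CR on the pre-surgery restaging scan versus baseline, in all randomized patients, with a missing scan counted as non-response.
- State a rule for patients without measurable disease at baseline, because the eligibility criteria in Section 3 do not require it. One option is to report the rate among those with measurable disease as well.
- State that no separate confirmatory scan is required, and that in resected patients post-operative scans count for recurrence, not response.
- Exempt this endpoint from 12.6.
- Report pathologic response (percent viability and pathologic complete response) separately, with resected patients as the descriptive denominator and pathologic complete response also shown over all randomized patients.
- Report later response in unresected patients separately.

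Besides 9.7.2 and 12.6, align the Synopsis objectives, 2.2, Study Calendar footnote 6 and 12.2.2, which now speak of best overall response or schedule the later response assessment.

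**Cost.** Wording only; the scan is already scheduled. The endpoint becomes a landmark, unconfirmed response instead of best overall response, slightly less stringent for want of confirmation and slightly conservative for missing scans. Keeping confirmation would also be valid but would need an added pre-surgery scan.
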